Subjects will be assigned post-injection blood draw at either 30 minutes, 45 minutes or 60 minutes after the gentamicin injection in a sequential fashion, meaning that participant #1 will have a 30 minute draw, #2 a 45 minute and #3 at 60 minute. This one green top tube of blood will be tested for gentamicin concentration as part of Objective 2 and Creatinine.

5. *Counseling:*

The study clinician will counsel the subject to avoid sexual activity, and most specifically performing oral sex, deep kissing, and oral-anal sex until they return for the TOC visit.

Test of Cure Visit

Subjects will return to the PHSKC STD Clinic to meet with the study clinician 4-7 days (+/- 1 day) after their enrollment visit. The study coordinator will call the subject the day prior to the visit as a reminder. At the TOC visit:

1. *Diagnostics:*

The study clinician will obtain a pharyngeal culture for *N. gonorrhoeae* and a blood draw for a follow-up creatinine. (Specimen processing per above). If the culture is positive for *N. gonorrhoeae*, the subject will be called to return for standard of care treatment – Ceftriaxone 250mg IM plus Azithromycin 1g orally once.

2. *Behavior and Symptom screen:*

The study clinician will administer a standardized symptom screening form (see Appendix F) to assess for gentamicin side effects and tolerability. The form will also ask about sexual activity, including kissing, in the time period between treatment and TOC.

Retention Plan

The study coordinator will attempt to schedule the TOC visit at 4 days after the enrollment visit so that if the subject fails to show to that visit, there are still opportunities to reschedule the TOC visit. Additionally, although the subject will be compensated for their time in the study, they will not receive compensation until they return for the TOC visit. This is an incentive for them to keep their follow-up visit.

Data Sources and Data Management

PHSKC STD Clinic Medical Record: We will use gonorrhea test results that occurred prior to enrollment visit from the STD clinic medical record for inclusion criteria. This data will be extracted by chart review during the enrollment visit using subject name and DOB as identifiers. The information will then be entered using a subject ID in the study database. We will also use demographic and sexual behavior data from the medical record.

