Neisseria Reference Laboratory: The NRL will provide the antimicrobial susceptibility data for the *N. gonorrhoeae* isolates recovered at both enrollment and TOC visit. The culture specimens are clinical specimens and full antimicrobial susceptibility testing (AST; this includes, beta-lactamase, penicillin, tetracycline, ciprofloxacin, cefixime, ceftriaxone, azithromycin and gentamicin) is done on all isolates. However, AST is not routinely reported to the clinic. Thus, in order to obtain this data, we will submit a list of names and MRN to [name], the Director of the NRL, to pull the data for us. All personal health information (PHI) will be transferred electronically using secure file transfer technology.

Data Entry Form: The study coordinator and study clinician will record key data points on a paper data entry form which will be transcribed into electronic data entry form in RedCap. Data to be collected will come from both the STD Clinic medical record and patient interview. Data points will include: date of visit, gender identity, sex assigned at birth, age, race, height, weight, site of infections pre-enrollment and type of test used to diagnosis; time of administration of gentamicin, time of gentamicin concentration blood draw; results of treatment visit testing (culture results at each site); date of TOC visit, symptoms since treatment; sexual activity since treatment (including kissing, oral-anal, oral-penile, anal-penile, penile-vaginal etc); anatomic sites tested by culture and results; repeat treatment needed etc (see Appendices E and F)

UW Lab Medicine Research Testing Services: RTS will test our blood specimens for pre- and post- treatment Creatinine and gentamicin levels. We will give the specimens to them with study id's and dates on them, and they will provide the data via an excel file with only study ID and results.

Data Management

We will use RedCap to collect and store all study data. Data can be exported from RedCap as a Stata database, which will be used for analysis. Upon export from RedCap, we will remove identifiers except for subject ID and maintain a separate database to link subject identifiers/contact info to subject ID.

Study Confidentiality and Security

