We will use study IDs to label data items that only pertain to the study – i.e. data entry form, aliquots for gentamicin level and creatinine. Specimens that are also clinical specimen, will be labeled with the patient's clinic label. Data will be obtained from the medical record and entered into the data entry form which will only be labeled with the Study ID. We will maintain a separate data base in RedCap that links the patient study ID and PHI. RedCap is 21 CFR part 11 compliant. We will destroy the link between the patient's identifying data and study ID after the study has been published or by December 31, 2021, whichever is sooner.

Laboratory Processing

Gentamicin & Creatinine levels:

Draw blood for enrollment day gentamicin level and baseline creatinine at 30, 45 or 60 minutes (timing to be pre-determined by sequential participants; i.e. participant 1 is drawn at 30 minutes, 2 at 45 minutes and 3 at 60 minutes) following administration of gentamicin 360mg IM. Use green top (sodium heparin) tube. Centrifuge and aliquot ~ 2mL into 5ml Sarstedt polypropylene tube. These will be transferred to freezer within 4 hours and frozen at -80 degrees celsius until transferred to UW RTS Lab in monthly batches. UW RTS determines peak Genatmicin levels using Enzyme Immunoassay Technique and Creatinine by Spectrophotometric technique.

N. gonorrhoeae cultures and Antimicrobial Susceptibility Testing

All gonorrhea cultures are clinical specimens. The PHSKC STD Clinic's policy is to collect specimens for *N. gonorrhoeae* culture from persons with 1) a NAAT positive test who are not yet treated (i.e. most of our subjects); 2) persons with symptoms of urethritis, or cervicitis; 3) persons who are a contact to gonorrhea, at all exposed anatomic sites; and 4) persons who need a test of cure (TOC). TOC are done for any person with a cefixime, ceftriaxone or azithromycin alert value MIC, or have pharyngeal gonorrhea treated with a non-ceftriaxone containing regimen (i.e. study subjects).

Clinical gonorrhea cultures are first sent to the PHSKC Laboratory for culture and identification, and *N. gonorrhoeae* isolates are then sent to the University of Washington's Neisseria Reference Laboratory (NRL) for antimicrobial susceptibility testing (AST) for surveillance purposes. Once a culture is identified as positive growth for gonorrhea, a report is made into the PHSKC STD Clinic medical record.

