The NRL first determines cefixime, ceftriaxone and azithromycin MIC by the etest method initially for prompt clinical action. Then, gonorrhea isolates undergo AST according to the Clinical and Laboratory Standards Institute (CLSI) recommended agar dilution method for further surveillance.[13] AST testing includes: Penicillin (PEN), Tetracycline (TET), Cefixime (CFM), Ceftriaxone (CRO), Ciprofloxacin (CIP), Azithromycin (AZM), and Gentamicin (GEN). We used CLSI[15] breakpoints to interpret MICs for penicillin ($\geq 2.0\mu\text{g/ml}$), tetracycline ($\geq 2.0\mu\text{g/ml}$), spectinomycin ($\geq 128.0\mu\text{g/ml}$), and ciprofloxacin ($\geq 1.0\mu\text{g/ml}$),[15] and used GISP alert values for azithromycin ($\geq 2.0\mu\text{g/ml}$), cefixime ($\geq 0.25\mu\text{g/ml}$), and ceftriaxone ($\geq 0.125\mu\text{g/ml}$) as CLSI has not established breakpoints for these antimicrobial agents.[12] Neither CLSI nor CDC have published breakpoints for gentamicin however, other institutes have used the following breakpoints that we will follow in this study: Resistant is $\geq 32\mu\text{g/ml}$; Intermediate susceptible 8-16 $\mu\text{g/ml}$, and Susceptible $\leq 4\mu\text{g/ml}$. Full AST results will be reported to the PI.

Data Safety and Monitoring Plan, Resolving & reporting Protocol Deviations, AEs and Unanticipated problems

OVERSIGHT RESPONSIBILITIES

Day-to-day oversight of the trial is provided by the Principal Investigator (PI), [name], along with [name] (co-I). [name] assures that informed consent is obtained prior to performing any research procedures, that all subjects meet eligibility criteria, and that the study is conducted according to the IRB-approved research plan. Drs. [name] and [name] review all study data and any adverse events (AEs) real-time, and report all SAEs to the Medical Monitor and IRB according to the approved DSMP.

Medical Monitor: Monitoring for the study will be provided by a volunteer Medical Monitor, [name], Professor of Medicine in the Division of Allergy and Infectious Diseases, who has over 25 years of experience with clinical trials, but is not directly related to the study team.

MONITORING PROCEDURES

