The Medical Monitor, [name], will review study conduct including efficacy and renal toxicity and AEs in aggregate on at a single interim analysis after 25 subjects, and at the end of the study. The Medical Monitor will review serious adverse events (SAEs), hearing loss, and serious drug allergies in real-time. Study data are provided to the Medical Monitor prior to the interim and final analysis. Data reports are prepared by the PI, [name].

MONITORING REPORT

The Medical Monitor, [name], will provide a written report to the study team with recommendations for study modification, study continuation/discontinuation as relevant. The study team is responsible for forwarding the report to the IRB.

COLLECTION AND REPORTING OF SAEs AND AEs

For this study, the following standard AE definitions are used:

Adverse event: Any unfavorable and unintended sign (including an abnormal laboratory finding), symptom or disease temporally associated with the use of a medical treatment or procedure, regardless of whether it is considered related to the medical treatment or procedure.

Serious Adverse Event: Any AE that results in any of the following outcomes:

- Death
- Life-threatening
- Event requiring inpatient hospitalization or prolongation of existing hospitalization
- Persistent or significant disability/incapacity

AEs are graded according to the following scale:

Mild: An experience that is transient, & requires no special treatment or intervention. The experience does not generally interfere with usual daily activities. This includes transient laboratory test alterations.

Moderate: An experience that is alleviated with simple therapeutic treatments. The experience impacts usual daily activities. Includes laboratory test alterations indicating injury, but without long-term risk.

Severe: An experience that requires therapeutic intervention. The experience interrupts usual daily activities. If hospitalization (or prolongation of hospitalization) is required for treatment it becomes an SAE.

The study uses the following AE attribution:

Not related: The AE is clearly not related to the study procedures (i.e., another cause of the event is most plausible and/or a clinically plausible temporal sequence is inconsistent with the onset of the event).

Possibly related: An event that follows a reasonable temporal sequence from the initiation of study procedures, but that could readily have been produced by a number of other factors.

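### Baseline creatinine is frozen for monthly shipment, so a subject's >40% rise is typically not knowable until about two weeks after dosing, and no repeat test or call-back is written for it

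*Combined protocol and SAP*

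**What the plan says.** Laboratory Processing (Gentamicin & Creatinine levels) describes one enrolment tube for both assays: "Draw blood for enrollment day gentamicin level and baseline creatinine at 30, 45 or 60 minutes" after the injection. The aliquot is then held: "These will be transferred to freezer within 4 hours and frozen at -80 degrees celsius until transferred to UW RTS Lab in monthly batches".

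For the TOC visit, Study Procedures asks for "a blood draw for a follow-up creatinine. (Specimen processing per above"). It does not say by name whether monthly batching applies to this sample. Data Sources sends both samples to one laboratory: "RTS will test our blood specimens for pre- and post- treatment Creatinine and gentamicin levels". On reporting, it says "they will provide the data via an excel file with only study ID and results". No turnaround time or alert value is given.

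The Data Analysis section treats a creatinine rise above 40% as significant. In the Data Safety and Monitoring Plan, the adverse event definition begins "Any unfavorable and unintended sign (including an abnormal laboratory finding"), and creatinine monitoring is named as one way events are identified. Under Oversight Responsibilities the investigators "review all study data and any adverse events (AEs) real-time". The Medical Monitor sees renal toxicity in aggregate at the interim and at the end. That role's real-time list covers serious events, hearing loss and serious allergic reactions, not creatinine.

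There are two study visits, and TOC is the second. The only call-back after it is for a positive culture, when "the subject will be called to return for standard of care treatment". The TOC form (Appendix F) has fields for cultures and susceptibility results but none for creatinine.

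**The concern.** A percentage rise needs both values, and the plan puts the first one in a freezer for up to a month. A subject whose creatinine has risen by more than 40% at TOC can therefore complete the last planned visit before anyone is able to know it. When the result does arrive, nothing written tells the team to repeat the test or contact the subject.

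Renal safety is part of Aim 2, and creatinine is the only toxicity with a numeric halting threshold. It also carries most of the renal safety check. Apart from the diagnosis of gonorrhoea, eligibility rests on self-report, and the baseline creatinine is drawn after the injection, so no laboratory value screens subjects before dosing. The adverse event scale separates transient laboratory changes from those indicating injury, and that distinction cannot be made from a single follow-up value with no recheck.

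**Working it through.** The plan states no reporting delay, so there is no figure of its own to reproduce. The check is date arithmetic.

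**Inputs**
- Baseline day = dosing day (day 0), because the tube is drawn 30, 45 or 60 minutes after injection (Laboratory Processing).
- TOC day T: 4 to 7, plus or minus 1, so day 3 to day 8. The Retention Plan aims for day 4.
- Shipping cycle: monthly, taken as 30 days (assumption; 28 to 31 checked below).
- Dosing days spread evenly over the cycle (assumption), so the wait W from dosing to the next shipment is Uniform(0, 30).
- Assay time: not given, set to 0. Any real assay time adds to every figure.

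**Case A: only the baseline is batched, and the TOC sample is assayed at once**

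The rise is knowable on day max(T, W), with maximum 30.
- Mean wait after TOC = (30 − T)²/60; maximum 30 − T.
- Mean time from dosing = T + (30 − T)²/60.
- Probability that the baseline is still unshipped at TOC = (30 − T)/30.

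| TOC day | Mean wait after TOC | Maximum wait after TOC | Mean from dosing | Baseline unshipped at TOC |
|---|---|---|---|---|
| 3 | 27²/60 = 12.15 | 27 | 15.15 | 27/30 = 90% |
| 4 | 26²/60 = 11.27 | 26 | 15.27 | 26/30 = 87% |
| 8 | 22²/60 = 8.07 | 22 | 16.07 | 22/30 = 73% |

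For a day-4 TOC, the wait after the visit exceeds 7 days for (30 − 11)/30 = 63% of subjects and 14 days for (30 − 18)/30 = 40%.

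**Case B: both samples are batched**

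The wait after TOC is itself Uniform(0, 30): mean 15, maximum 30. It exceeds 7 days for 23/30 = 77% and 14 days for 16/30 = 53%.
- Day-4 TOC: mean from dosing 4 + 15 = 19 days, maximum 34.
- Day-8 TOC: mean 8 + 15 = 23 days, maximum 8 + 30 = 38.

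**Sensitivity to the cycle length**

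With 28 to 31 days, the maximum from dosing is 28 to 31 days in case A, and 36 to 39 days in case B with a day-8 TOC.

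**Under the fix**

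If the pair is sent together on a weekly run after TOC, the wait after the visit is at most 7 days, with a mean of 3.5.

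**The case against.** Several stronger readings are tempting, and the documents do not support them.

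- A reader might infer that batching breaks the promise of real-time review. That phrase can fairly mean review as results arrive, and it sets no turnaround. What stands is that such review cannot begin until the batch is run.
- A reader might infer that nothing in the plan handles a creatinine event. The Data Safety and Monitoring Plan sends serious events and certain procedure-related events to the Medical Monitor within 24 hours, and refers all events to the university's reporting guidelines. The procedure-related events are not listed and the guidelines are not reproduced, so a creatinine rise may or may not be covered. These are reporting rules; neither states a repeat test or a call-back.
- A reader might infer that the renal stopping rule will be judged on incomplete data. Enrolment pauses at each look and the rules at those looks include creatinine, so the natural reading is that the team can wait for results.
- A reader might take 38 days as the usual delay. It needs a day-8 TOC, a just-missed shipment and batching of the TOC sample.

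The case for leaving the plan alone is that creatinine is being used as a group safety endpoint. The dose is single, so no later dose could be withheld from the affected subject. Subjects with renal disease, diabetes or nephrotoxic drugs are excluded, and a transient laboratory change is graded mild. No accrual rate is given, so the number dosed during a wait cannot be stated. All of this stands and limits the consequence. It does not explain why a change the plan itself calls significant should have no individual follow-up when providing it is cheap. The separate list linking study IDs to identities makes a call-back feasible.

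**Conclusion.** The point holds as a low-cost improvement to subject follow-up; it does not undermine the trial's results. Because the baseline creatinine is batched monthly, a >40% rise becomes knowable on average 15 to 16 days and at most 30 days after dosing, or a mean of 11 days after a day-4 TOC. If the TOC sample is batched too, the mean is about 19 days for a day-4 TOC and the maximum 38 days for a day-8 TOC. The shared laboratory and the cross-reference to processing favour that reading but do not settle it. All figures assume a 30-day cycle, evenly spread dosing and zero assay time.

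The absence of a recheck or call-back is confirmed for the text reviewed, which did not include the consent pages or Appendices B and C (the info and reminder cards). What is gained is follow-up of the affected subject and an earlier signal to the investigators.

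**What to change.** 1. **Laboratory Processing:** split the baseline plasma into two aliquots. Keep gentamicin in monthly batches. Send each subject's baseline and TOC creatinine together soon after TOC, weekly at the latest, with a turnaround agreed with the laboratory. State under Test of Cure Visit, Diagnostics that this covers the TOC sample, which is drawn for creatinine only and needs no split.
2. **Test of Cure Visit, Diagnostics:** add that a rise above 40% triggers a call-back for a repeat creatinine and notice to the Medical Monitor.
3. **Optional clarification in the interim analysis text** (Data Analysis Plans and Data Analysis): state that paired creatinine results must be in hand before the renal rule is judged, using an off-cycle shipment if needed. The existing pause already allows this.

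**Cost:** the number of planned creatinine tests does not change (2 × 60 = 120). Weekly shipment means about 52/12 = 4.3 times as many courier trips, and small runs may carry a higher unit price. There is one extra tube per subject, at baseline only, and an extra draw and visit only for a subject with a >40% rise. Sending the pair together also allows both values to be measured in one assay run.

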Related: The AE is clearly related to the study procedures.

AEs are identified at the TOC visit using the symptom screen, and with Creatinine monitoring.

SAEs and specific procedure-associated AEs are reported to the Medical Monitor within 24 hours. In addition, all AEs are reported according to the University of Washington AE reporting guidelines.

MANAGEMENT OF RISKS TO SUBJECTS

Expected AEs

Expected AEs associated with gentamicin include:

- Pain at injection site
- Bruising at injection site

AE Management

- Warm compresses as needed
- Tylenol as needed

DATA ANALYSIS PLANS

The Medical Monitor will conduct interim analyses after we have primary outcome results for 10 and 25 subjects. (Enrollment will pause until analyses can be conducted). Stopping rules include the primary end point (i.e. pharyngeal cure rate), and adverse events. If after 10 and 25 subjects, the cure rate is $\leq 44\%$ (99% CI 17% – 74%; i.e. 11 persons of 25 persons with a positive culture on treatment date fail treatment), we will stop the study. We chose these numbers using the O'Brien-Fleming method of alpha spending for multiple analyses, assuming an alpha of 0.003 for the first analysis and an alpha of 0.049 for the final analysis. Using the 99% CI obtained with 11/25 treatment failures, the upper bound is less than 75%. (Our hypothesis is that gentamicin alone will be 80% effective for pharyngeal gonorrhea, with the goal to use it in combination with a second agent). Alternatively, if at interim analysis more than 20% of subjects (99% CI 20% - 46%) have a greater than 40% increase in their creatinine from baseline, we will halt the study.

Data Analysis

The proposed study aims to evaluate the efficacy of a single intramuscular (IM) dose of 360 mg of gentamicin in the treatment of pharyngeal gonorrhea. Secondary objectives include evaluating the renal safety and tolerability of 360mg of gentamicin, *documenting peak serum gentamicin levels by subject weight*, and estimating the ideal pharmacodynamic criterion using a combination of peak gentamicin concentration levels compared to MIC and treatment outcomes. *In exploratory analyses*, we will attempt to determine whether gentamicin-monotherapy induces antimicrobial resistance among treatment failures. The specific aims are:

- 1) Determine the proportion of persons whose pharyngeal gonococcal infections are cured with a single dose of 360mg gentamicin intramuscularly alone.

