- 2) Evaluate the renal safety and tolerability of 360mg IM of gentamicin.
- 3) Document mean peak gentamicin levels following 360mg IM of gentamicin stratified by weight.
- 4) Estimate the best pharmacodynamics criterion (i.e. peak/MIC ratio) for pharyngeal gonorrhea treated with gentamicin *using individual* and mean peak gentamicin levels and NG isolate MIC.
- 5) Among treatment failures, *conduct exploratory analyses* comparing pre- and post-treatment MIC for evidence of induced resistance.

Analyses

The primary endpoint is the pharyngeal cure rate – that is, the proportion of subjects who return for TOC who clear their infections as evidenced by a negative culture 4-7 (+/-1) days after treatment. The cure rate will be calculated as the number of cured subjects divided by the total number of subjects who received treatment and returned for follow-up testing in a modified an intention to treat (mITT) analysis. We will also calculate the 95% CI for this proportion.

$$\text{Cure rate} = \frac{\text{number of subjects with negative pharyngeal culture at TOC}}{\text{number of subjects with + throat test at enrollment \& received gentamicin}}$$

Persons who test negative for NG at their enrollment visit (i.e. infection cleared between initial clinical screening test and enrollment) will be excluded from analysis. Treatment failure will be defined as a positive culture 4-7 (+/-1) days after treatment.

For our second objective, we will obtain pre- and post-treatment serum creatinine. An elevation of >40% will be considered significant. We will evaluate subject's tolerability (Obj. 2) using a standardized symptom questionnaire (see Appendix F) conducted at the TOC visit. The symptoms questioned will include, but not be limited to, rash, tinnitus, decreased hearing, nausea, vomiting, diarrhea, headaches, and decreased appetite. There will also be a section for free response.

Our third objective is to document the pharmacokinetics of 360mg of IM gentamicin by weight. We will obtain serum gentamicin levels at 30, 45 and 60minutes post dosing based on previous studies that estimated that IM gentamicin peaks between 30-60 minutes post-dose.

We will stratify the results by time post-dose, as well as by subject weight in kilograms (categorized).

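### Between the 25-subject look and study end, the Medical Monitor has no scheduled renal review and no clearly stated route to creatinine rises above 40% that are not SAEs

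*Combined protocol and SAP*

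**What the plan says.** All references are to the combined protocol and SAP.

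- **Aggregate review.** Monitoring Procedures, in the Data Safety and Monitoring Plan (DSMP), provides for the Monitor's review of "efficacy and renal toxicity and AEs in aggregate on at a single interim analysis after 25 subjects, and at the end of the study". It adds: "Study data are provided to the Medical Monitor prior to the interim and final analysis".
- **Real-time review.** In the same place, the Monitor "will review serious adverse events (SAEs), hearing loss, and serious drug allergies in real-time". Creatinine is not named.
- **Renal threshold.** The Analyses part of Data Analysis states: "An elevation of >40% will be considered significant". The DSMP's Data Analysis Plans begins its halting rule "Alternatively, if at interim analysis more than 20% of subjects". Data Analysis ties its own version, 32% or more, to the interim analysis too. The summary SAP gives a 20% rule without a date, beside its interim look.
- **Timing of looks.** Monitoring Procedures and the summary SAP name 25 subjects only. The DSMP's Data Analysis Plans and Data Analysis name 10 and 25. None names a later one.
- **Other oversight.** Adverse events are found as follows: "AEs are identified at the TOC visit using the symptom screen, and with Creatinine monitoring". Oversight Responsibilities has the investigators look at all data and adverse events as they occur and pass SAEs to the Monitor. The AE reporting text also sends the Monitor, within 24 hours, an undefined class of procedure-associated events, and puts all adverse events under university guidelines that are not reproduced.
- **Laboratory timing.** Laboratory Processing has frozen samples go for creatinine assay in monthly batches.

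**The concern.** Renal toxicity is the only adverse event with a numeric halting threshold, and renal safety is part of the second specific aim. Hearing loss reaches the Monitor in real time whether or not it is an SAE; a creatinine rise above 40% is not given that treatment. The SAE definition covers death, threat to life, hospitalization and disability, so such a rise need not qualify.

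If the true rate were high but the first 25 subjects happened to fall below the threshold, the reviewer outside the study team would not be scheduled to see the renal count again until everyone had been dosed. Each subject receives one dose, so a later review can protect only those not yet enrolled.

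**Working it through.** **1. The plan's own figure.** The summary SAP gives 7–40% as the 95% interval for its 20% rule. The exact (Clopper-Pearson) interval for 5 of 25 runs from the 0.025 quantile of Beta(5, 21) to the 0.975 quantile of Beta(6, 20), which is 6.8% to 40.7%. The match supports reading that undated rule as a 25-subject rule.

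**2. Subjects after the last scheduled check.** 60 − 25 = 35, and 35/60 = 58%. This is an upper bound, because the look waits for 25 primary outcomes. Data Analysis assumes 40 cures at an 80% cure rate, so 40/0.80 = 50 evaluable subjects. If 50 of 60 are evaluable, about 25 × 60/50 = 30 are enrolled at the look and 30 remain.

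**3. Thresholds as counts.** More than 20% means at least 6 of 25 (3 of 10). At least 32% means at least 8 of 25 (4 of 10).

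**4. Method.** The documents give neither a true renal event rate nor an accrual rate, so both the rates and the tally spacing are assumptions. The calculation is an exact recursion on the cumulative count. At each tally of size L, add the new Binomial(subjects since last tally, p) count, then remove the probability at or over the threshold; the amount removed is P(stop at L). Then

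E(dosed) = Σ P(stop at L) × L + P(no stop) × 60,

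and the saving is E(dosed) under the planned looks minus E(dosed) with tallies added. Every crossing is assumed to stop dosing. For a reporting delay of d subjects, L becomes min(L + d, 60) at tallies after 25. No delay applies at 10 or 25, because enrollment pauses there.

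**5. Tallies at 30, 35, … 55, no delay.** Differences are taken before rounding. The rows with two looks assume the renal rule is applied at both.

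| Threshold | True rate | Planned looks | P(cross), planned looks | Added P(cross) | Subjects spared |
|---|---|---|---|---|---|
| >20% | 25% | 25 | 0.62 | 0.23 | 4.9 (38.2 to 33.3) |
| >20% | 25% | 10, 25 | 0.69 | 0.18 | 3.8 |
| >20% | 30% | 25 | 0.81 | 0.16 | 3.6 (31.8 to 28.2) |
| >20% | 30% | 10, 25 | 0.85 | 0.12 | 2.7 |
| ≥32% | 25% | 25 | 0.27 | 0.08 | 1.5 (50.4 to 48.9) |
| ≥32% | 25% | 10, 25 | 0.36 | 0.06 | 1.2 |
| ≥32% | 30% | 25 | 0.49 | 0.14 | 2.6 (42.9 to 40.3) |
| ≥32% | 30% | 10, 25 | 0.56 | 0.11 | 2.1 |

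**6. Wider batches and delay, both planned looks kept.** With tallies every 10 or 15 subjects and no delay, the more-than-20% saving is 3.0 or 2.4 at a true 25%, and 2.2 or 1.8 at 30%. With a delay of 5 to 10 subjects it is 1.0 to 2.2 and 0.8 to 1.6. Under the 32% threshold with that delay it is 0.3 to 0.9 across both rates.

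**7. Unneeded prompts (25-subject look, then every 5).** Under more than 20%, the tallies add a crossing probability of 0.02 at a true 10%, 0.10 at 15% and 0.21 at 20%. Under 32% or more they add less than 0.001, 0.003 and 0.02.

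**The case against.** The strongest reply is that this is a design choice in a 60-person, single-dose study that excludes renal disease, diabetes and nephrotoxic drugs. The investigators already see every result, and nothing in the documents requires continuous independent review of laboratory changes that are not SAEs. The gain is a few subjects at most, and only at toxicity rates the documents do not suggest. All of that stands, and it sets the weight of the point. It does not show that the Monitor will see these rises.

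Three stronger readings are tempting, and the documents support none of them.

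- **That renal safety goes unmonitored after 25 subjects.** It does not. Creatinine is still measured, a rise is identified as an adverse event, and the investigators review it.
- **That the Monitor has no route at all to such rises.** The 24-hour rule for procedure-associated events might cover them, since the attribution scale uses study procedures for all causation. But the class is undefined, creatinine is not named, and the injection-site events listed next could suggest a narrower meaning. The route is unclear rather than absent, and it supplies no running count.
- **That later tallies would usually catch what the 25-subject look missed.** Under more than 20%, the probability of a later crossing, given that the look is passed, is (0.852 − 0.622)/(1 − 0.622) = 0.61 at a true 25%, and 0.82 at 30%. Those figures are conditional. The planned look alone already crosses with probability 0.62 and 0.81, so the unconditional gain is only 0.23 and 0.16. Under 32% or more even the conditional figures are 0.10 and 0.27.

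**Conclusion.** The gap is real and narrow. For up to 35 of 60 subjects, the Monitor has no scheduled aggregate renal review, no threshold check and no clearly stated route to a creatinine rise above 40% that is not an SAE.

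The expected benefit of closing it is modest: upper bounds of 1.2 to 4.9 subjects spared with frequent, undelayed tallies, and about 0.3 to 2.2 under more realistic batching and delay. The range depends on the threshold, on whether the 10-subject look is kept and on the assumed true rates of 25% and 30%. These figures also treat every crossing as a stop, which the change below does not require. This is a low-cost suggested improvement, not a defect that undermines the trial.

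**What to change.** Keep the planned looks and their halting rules. In Monitoring Procedures:

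1. Add a creatinine rise of more than 40% from baseline to the events the Monitor reviews in real time, counted from receipt of the batch result. This also settles whether the 24-hour class covers it.
2. With each laboratory batch after the 25-subject look, send the Monitor the cumulative number of such rises over the number of dosed subjects with both creatinine values. If the proportion crosses the renal threshold, the Monitor reviews and advises through the existing written report, which already provides for "recommendations for study modification, study continuation/discontinuation as relevant". It is not an automatic halt. The threshold is reused at each tally without adjustment, so it can serve only as a prompt.

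Step 2 needs one threshold, so the 20% and 32% versions must first be reconciled.

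The cost is protocol wording, one tally per batch and individual notices, with no new samples. If all 60 subjects have both values, expected notices are 60 × p: 3 at a true 5%, 6 at 10% and 18 at 30%. Some will be rises of the kind the AE scale grades as mild ("This includes transient laboratory test alterations"). Occasional unneeded reviews will follow, with an added probability of about 0.02 at a true 10% under the more-than-20% threshold.
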